**Table 8 Estimated Power and Sample Size Table**

Analyte	Parameter	n	CVw%	Power
EE	AUC(0-inf)	16	11.5	99.98
	Cmax	16	12.5	99.87
LNG	AUC(0-inf)	16	14.9	98.66
	C max	16	17.9	92.73
Joint Power for all 4 comparisons		16		91.91

Table 9 provides the 90% CIs for a range of possible observed ratios, for each assumed CVw%, with 16 estimated participants.

**Table 9 Sample Size: Estimated Precision for Different Observed Effects**

Analyte	Parameter	n	CVw%	Observed Ratio	Estimated 2-sided 90% CI
EE	AUC (0-inf)	16	11.5	0.90	(0.84, 0.97)
				1.0	(0.93, 1.07)
				1.10	(1.02, 1.18)
	C max	16	12.5	0.90	(0.83, 0.97)
				1.0	(0.93, 1.08)
				1.10	(1.02, 1.19)
LNG	AUC (0-inf)	16	14.9	0.90	(0.82, 0.99)
				1.0	(0.91, 1.10)
				1.10	(1.00, 1.21)
	C max	16	17.9	0.90	(0.81, 1.01)
				1.0	(0.90, 1.12)
				1.10	(0.98, 1.23)

### 9.5.1. Calculation of CVw from CI:

The point estimate (PE, adjusted geometric mean) and the confidence interval limits have been obtained from historical reference.

The number of subjects / sequence (example 2×2 cross-over), is obtained as follows:

- If total sample size (N) is an even number, assume  $n_1 = n_2 = \frac{1}{2}N$
- If N is an odd number, assume  $n_1 = \frac{1}{2}N + \frac{1}{2}$ ,  $n_2 = \frac{1}{2}N - \frac{1}{2}$  (not  $n_1 = n_2 = \frac{1}{2}N$ )

The difference between the CL and the PE can be calculated as follows on the log-scale (using the CL which is given with the highest number of significant digits).

$$\Delta_{CL} = \ln (CL_{hi}) - \ln(PE) \text{ |or| } \Delta_{CL} = \ln(PE) - \ln (CL_{lo})$$

The Mean Square Error (MSE) is then calculated as follows:

$$MSE = 2 \left( \frac{\Delta_{CL}}{\sqrt{\left( \frac{1}{n_1} + \frac{1}{n_2} \right)} \times t_{(1-2\alpha, n_1+n_2-2)}} \right)^2$$

And finally, the CVw is calculated from the MSE:

$$CVw\% = 100 \times \sqrt{e^{MSE} - 1}$$

## 10. SUPPORTING DOCUMENTATION AND OPERATIONAL CONSIDERATIONS

### 10.1. Appendix 1: Regulatory, ethical, and study oversight considerations

#### 10.1.1. Regulatory and ethical considerations

- This study will be conducted in accordance with the protocol and with the following:
  - Consensus ethical principles derived from international guidelines including the Declaration of Helsinki and CIOMS international ethical guidelines
  - Applicable ICH GCP guidelines
  - Applicable laws and regulations
- The protocol, protocol amendments, ICF, IB, and other relevant documents (e.g., advertisements) must be submitted to an IRB/IEC by the investigator and reviewed and approved by the IRB/IEC before the study is initiated.
- **Any amendments to the protocol will require IRB/IEC approval before implementation of changes made to the study design, except for changes necessary to eliminate an immediate hazard to study participants.**
- Protocols and any substantial amendments to the protocol will require health authority approval prior to initiation except for changes necessary to eliminate an immediate hazard to study participants.
- The investigator will be responsible for the following, as applicable:
  - Providing written summaries of the status of the study to the IRB/IEC annually or more frequently in accordance with the requirements, policies, and procedures established by the IRB/IEC
  - Notifying the IRB/IEC of SAEs or other significant safety findings as required by IRB/IEC procedures
  - Providing oversight of the conduct of the study at the site and adherence to requirements of 21 CFR, ICH guidelines, the IRB/IEC, European regulation

536/2014 for clinical studies (if applicable), and all other applicable local regulations

#### **10.1.2. Financial disclosure**

Investigators and sub-investigators will provide the sponsor with sufficient, accurate financial information as requested to allow the sponsor to submit complete and accurate financial certification or disclosure statements to the appropriate regulatory authorities. Investigators are responsible for providing information on financial interests during the course of the study and for 1 year after completion of the study.

#### **10.1.3. Informed consent process**

- The investigator or the investigator's representative will explain the nature of the study, including the risks and benefits, to the participants and answer all questions regarding the study.
- Potential participants must be informed that their participation is voluntary. They will be required to physically or digitally sign a statement of informed consent that meets the requirements of 21 CFR 50, local regulations, ICH guidelines, HIPAA requirements, privacy and data protection requirements, where applicable, and the IRB/IEC or study center.
- The medical record must include a statement that physical or digital informed consent was obtained before the participant was enrolled in the study and the date the physical or digital consent was obtained. The authorized person obtaining the informed consent must also sign the ICF.
- Participants must be reconsented to the most current version of the ICF(s) during their participation in the study.
- A physical or digital copy of the ICF(s) must be provided to the participant.

In case of unexpected pregnancy, participant must be informed that PI such as date of birth, sex of the baby will be collected as part of safety follow-up. Consent for the baby may be obtained from the participant and/or their partner as per local regulations.

#### **10.1.4. Recruitment strategy**

Participants will be identified for potential recruitment using clinical database and IEC/IRB-approved advertisements (e.g., newspaper, social media) prior to consenting to take part in this study.

#### **10.1.5. Data protection**

- Participants will be assigned a unique identifier by the investigator. Any participant records or datasets that are transferred to the sponsor will contain the identifier only; participant names or any information which would make the participant identifiable will not be transferred.

- GSK will ensure protection of the personal data of the investigator and site staff which is collected within the framework of and for the purpose of the study.
- The participant must be informed that their personal study-related data will be used by the sponsor in accordance with local data protection law. The level of disclosure must also be explained to the participant, that their data will be used as described in the informed consent.
- The participant must be informed that their medical records may be examined by Clinical Quality Assurance auditors or other authorized personnel appointed by the sponsor, by appropriate IRB/IEC members, and by inspectors from regulatory authorities.
- The contract between sponsor and study sites specifies responsibilities of the parties related data protection, including handling of data security breaches and respective communication and cooperation of the parties.
- Information technology systems used to collect, process, and store study-related data are secured by technical and organizational security measures designed to protect such data against accidental or unlawful loss, alteration, or unauthorized disclosure or access. GSK and/or trusted third parties working on behalf of GSK and/or institutions working with GSK for the purposes of this study are contractually bound to protect participant coded data. GSK will protect participant coded data and will only share it as described in the ICF.n

#### **10.1.6. Committees structure**

A SRT is in place for each GSK product. It comprises of a global cross-functional team responsible for the ongoing assessment of benefit-risk for a product. The SRT contribute to the continual assessment of incoming new efficacy and safety information.

#### **10.1.7. Dissemination of Clinical Study Data**

- The key design elements of this protocol and results summaries will be posted on [www.ClinicalTrials.gov](http://www.ClinicalTrials.gov) and/or GSK Clinical Study Register in compliance with applicable regulations/GSK policy. GSK will aim to register protocols summaries prior to study start and target results summaries submission within 12 months of primary/ study completion date. Where external regulations require earlier disclosure, GSK will follow those timelines.
- Where required by regulation, summaries will also be posted on applicable national or regional clinical study registers.
- Where required by applicable regulatory requirements, an investigator signatory will be identified for the approval of the study report, and provided reasonable access to statistical tables, figures, and relevant reports. GSK will also provide the investigator with the full summary of the study results, including a summary of trial results understandable to laypersons. The investigator is encouraged to share the plain language summary with the study participants, as appropriate. The full study report will be made available upon request, after decision on marketing authorization by regulatory authorities.

- GSK will provide the investigator with the randomization codes and participant-level line listings for their site only after completion of the full statistical analysis.
- GSK intends to make anonymized participant-level data from this study available to external researchers for scientific analyses or to conduct further research that can help advance medical science or improve patient care. This helps ensure the data provided by study participants are used to maximum effect in the creation of knowledge and understanding.

#### **10.1.8. Data quality assurance**

- All participant data relating to the study will be recorded on printed or electronic CRFs unless transmitted to the sponsor or designee electronically (e.g., laboratory data). The investigator is responsible for verifying that data entries are accurate and correct by physically or electronically signing the CRF.
- **Guidance on completion of eCRFs will be provided in eCRF completion guidelines.**
- The investigator must permit study-related monitoring, audits, IRB/IEC review, and regulatory agency inspections and provide direct access to source documents.
- QTLs will be predefined in the QTL plan to identify systematic issues that can impact participant right, safety and/or reliability of study results. These predefined parameters will be monitored during the study, and important deviations from the QTLs and remedial actions taken will be summarized in the CSR.
- Monitoring details describing strategy, including definition of study critical data items and processes (e.g., risk-based initiatives in operations and quality such as risk management and mitigation strategies and analytical risk-based monitoring, involvement of central reading mechanism) methods, responsibilities, and requirements, including handling of noncompliance issues and monitoring techniques (central, remote, or on-site monitoring) are provided in the monitoring plan .
- The sponsor or designee is responsible for the data management of this study, including quality checking of the data.
- The sponsor assumes accountability for actions delegated to other individuals (e.g., contract research organizations).
- Records and documents, including signed ICF, pertaining to the conduct of this study must be retained by the investigator for 25 years from the issue of the final CSR/ equivalent summary unless local regulations or institutional policies require a different retention period. No records may be destroyed during the retention period without the written approval of the sponsor. No records may be transferred to another location or party without written notification to the sponsor.
- When copies of source documents are shared with external third parties contracted by GSK for review by a central reader mechanism (e.g., endpoint adjudication committee; expert reader), documents are stored by the external body for a minimum of 7 years. These documents will be used by the third party solely for the purpose indicated within this protocol.

### 10.1.9. Source documents

- Source documents provide evidence for the existence of the participant and substantiate the integrity of the data collected. Source documents are filed at the investigator's site.
- Data reported on the eCRFor entered in the eCRF that are transcribed from source documents must be consistent with the source documents or the discrepancies must be explained. The investigator may need to request previous medical records or transfer records, depending on the study. Also, current medical records must be available.
- Definition of what constitutes source data and its origin can be found in source data acknowledgment.
- The investigator must maintain accurate documentation (source data) that supports the information entered in the eCRF.
- The sponsor or designee will perform monitoring to confirm that data entered into the eCRF by authorized site personnel are accurate, complete, and verifiable from source documents; that the safety and rights of participants are being protected; and that the study is being conducted in accordance with the currently approved protocol and any other study agreements, ICH GCP, and all applicable regulatory requirements.
- Copies of documents are shared with external third parties contracted by GSK for review by a central reader mechanism (e.g. endpoint adjudication committee; expert reader). The non-exhaustive list of documents shared to inform the central reader may include, discharge summaries, imaging reports, ECG reports etc. Participant names or any information which would make the participant identifiable or is not essential for the central reader mechanism will be redacted by the investigator sites prior to transfer. Details of the list of documents and the redaction procedure are provided in the site manual or equivalent. These documents will be used by the third party solely for the purpose indicated within this protocol.

### 10.1.10. Study and site start and closure

#### Start of study and first act of recruitment

The start of study and the first act of recruitment are defined as FSFV (first ICF signature date) at a country-level.

#### Study/Site Termination

GSK or designee reserves the right to close the study site or terminate the study at any time for any reason at the sole discretion of GSK. Study sites will be closed upon study completion. A study site is considered closed when all required documents and study supplies have been collected and a study-site closure visit has been performed.

The investigator may initiate study-site closure at any time, provided there is reasonable cause and sufficient notice is given in advance of the intended termination.

Reasons for the early closure of a study site by the sponsor or investigator may include but are not limited to:

**For study termination:**

- Discontinuation of further study intervention development

**For site termination:**

- Failure of the investigator to comply with the protocol, the requirements of the IRB/IEC or local health authorities, the sponsor's procedures, or GCP guidelines
- Inadequate or no recruitment (evaluated after a reasonable amount of time) of participants by the investigator
- Total number of participants included earlier than expected

If the study is prematurely terminated or temporarily suspended, the sponsor shall promptly inform the investigators, the IECs/IRBs, the regulatory authorities, and any contract research organization(s) used in the study of the reason for termination or temporary suspension, as specified by the applicable regulatory requirements. The investigator shall promptly inform the participant and should assure appropriate participant therapy and/or follow-up.

### **10.1.11. Publication policy**

The results of this study may be published in peer reviewed scientific literature and/or presented at scientific meetings. The sponsor will comply with the requirements for publication of study results in accordance with standard editorial and ethical practice and as per the sponsor's internal policy. Authorship will be determined by mutual agreement and in line with ICMJE authorship requirements.

## **10.2. Appendix 2: Clinical laboratory tests**

- The tests detailed in [Table 10](#) will be performed by the local laboratory.
- Protocol-specific requirements for inclusion or exclusion of participants are detailed in Section [5](#) of the protocol.
- Additional tests may be performed at any time during the study as determined necessary by the investigator or required by local regulations.
- Investigators must document their review of each laboratory safety report.

**Table 10 Protocol-required safety laboratory tests**

Laboratory Tests	Parameters
Haematology	Platelet count Red blood cell (RBC) count RBC indices: Mean corpuscular volume (MCV) Mean corpuscular hemoglobin (MCH) Hemoglobin Hematocrit %Reticulocytes WBC count with differential: Neutrophils Lymphocytes Monocytes Eosinophils Basophils
Clinical chemistry	Aspartate aminotransferase (AST)/serum glutamic-oxaloacetic transaminase (SGOT) Alanine aminotransferase (ALT)/serum glutamic-pyruvic transaminase (SGPT) Alkaline phosphatase  Total bilirubin Direct bilirubin Total protein Blood urea nitrogen (BUN)/Urea Potassium Creatinine* Sodium Calcium Glucose [indicate if fasting or nonfasting] Creatine phosphokinase (CPK) Homocysteine Antiphospholipid antibodies Sex hormone binding globulin (SHBG)
Routine urinalysis	Specific gravity pH, glucose, protein, blood, ketones, [bilirubin, urobilinogen, nitrite, leukocyte esterase] by dipstick Microscopic examination (if blood or protein is abnormal) Epithelial cells Red Blood cells WBC Casts Crystals Culture (if positive: specify pathogen)
Pregnancy testing	Highly sensitive [serum or urine] human chorionic gonadotropin (hCG) pregnancy test (as needed for WOCBP) 

Laboratory Tests	Parameters
Other screening tests	Follicle stimulating hormone and estradiol (as needed in WONCBP only) [Serum or urine] [alcohol and drug screen (to include at minimum: amphetamines, barbiturates, cocaine, cotinine, opiates, cannabinoids and benzodiazepines)] [Serology [(HIV antibody 4th generation test, HBsAg, and HCV antibody)] SHBG

NOTES:

1. Details of liver chemistry stopping criteria and required actions and follow-up are given in Section 7.1.1 :Liver Chemistry Stopping Criteria and Section 10.4: Liver Safety: Suggested Actions and Follow-up Assessments [and Study Intervention Rechallenge Guidelines]]. All events of ALT [or AST]  $\geq 3 \times$  ULN and total bilirubin  $\geq 2 \times$  ULN ( $> 35\%$  direct bilirubin) or ALT [or AST]  $\geq 3 \times$  ULN and INR  $> 1.5$  (if INR measured), which may indicate severe liver injury (possible Hy's law), must be reported to [sponsor] in 24 hours (excluding studies of hepatic impairment or cirrhosis).
2. If alkaline phosphatase is elevated, consider fractionating.
3. Local urine testing will be standard for the protocol unless serum testing is required by local regulation or IRB/IEC

\* To assess the kidney function, use the eGFR 2021 calculator

## 10.3. Appendix 3: AEs and SAEs: Definitions and procedures for recording, evaluating, follow-up, and reporting

### 10.3.1. Definition of AE

AE definition

 
• An AE is any untoward medical occurrence in a clinical study participant, temporally associated with the use of a study intervention, whether or not considered related to the study intervention.
 
• NOTE: An AE can therefore be any unfavorable and unintended sign (including an abnormal laboratory finding), symptom, or disease (new or exacerbated) temporally associated with the use of a study intervention.
 

Events Meeting the AE Definition

 
• Any abnormal laboratory test results (haematology, clinical chemistry, or urinalysis) or other safety assessments (e.g., ECG, radiological scans, vital signs measurements), including those that worsen from baseline, considered clinically significant in the medical and scientific judgment of the investigator (i.e., not related to progression of underlying disease).
 
• Exacerbation of a chronic or intermittent pre-existing condition including either an increase in frequency and/or intensity of the condition.
 
• New condition detected or diagnosed after study intervention administration even though it may have been present before the start of the study.
 
• Signs, symptoms, or the clinical sequelae of a suspected intervention- intervention interaction.
 

- Signs, symptoms, or the clinical sequelae of a suspected overdose of either study intervention or a concomitant medication. Overdose per se will not be reported as an AE/SAE unless it is an intentional overdose taken with possible suicidal/self-harming intent. Such overdoses should be reported regardless of sequelae.
- Events that occur as a result of protocol-mandated procedures (i.e. invasive procedures, modification of participant's previous therapeutic regimen).

Events NOT Meeting the AE Definition

- Any clinically significant abnormal laboratory findings or other abnormal safety assessments that are associated with the underlying disease, unless judged by the investigator to be more severe than expected for the participant's condition.
- The disease/disorder being studied or expected progression, signs, or symptoms of the disease/disorder being studied, unless more severe than expected for the participant's condition.
- Medical or surgical procedure (e.g., endoscopy, appendectomy): the condition that leads to the procedure is the AE.
- Situations in which an untoward medical occurrence did not occur (social and/or convenience admission to a hospital, admission for routine examination.).
- Anticipated day-to-day fluctuations of pre-existing disease(s) or condition(s) present or detected at the start of the study that do not worsen. Pre-existing diseases will be recorded in the medical history section of the eCRF.
- Hospitalization for elective treatment of a pre-existing condition (known or diagnosed before signing the informed consent) that did not worsen from baseline.
- The event is, in the investigator's opinion, of greater intensity, frequency, or duration than expected for the individual participant, or
- The investigator considers that there is a reasonable possibility that the event was related to the administration of the study intervention

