**Adverse Events/ Serious Adverse Events, Clinical laboratory assessments, ECG, and Vital Sign measurements:**

- Population: Healthy female participants of non-childbearing potential aged 18 to 65 years.
- Endpoints:
  - Incidence of serious adverse events within each treatment period.
  - Incidence of adverse events of grade 3 severity or higher within each treatment period.
  - Incidence of adverse events considered by the investigator to be possibly, probably or definitely related to study drug (overall and separately for Microgynon and GSK3036656) within each treatment period.
  - Incidence of participants withdrawn from the treatment/study due to adverse events within each treatment period.
  - Incidence of ECG values of PCI within each treatment period.
  - Incidence of clinical chemistry laboratory values of PCI within each treatment period.
  - Incidence of haematology laboratory values of PCI within each treatment period.
  - Incidence of vital signs parameters of SBP, DBP and HR of PCI within each treatment period.
- Treatments: single dose Microgynon, once daily GSK3036656 and single dose Microgynon +once daily GSK3036656
- Strategy for intercurrent event: The intercurrent events of interest are participants missing the dose of Microgynon, missing one or more doses of GSK3036656 or discontinuing GSK3036656 early due to any reason. The strategy for handling these intercurrent events will be a Treatment Policy Strategy, where all safety data after the intercurrent event will be included.
- Population-level summary: Frequency and percentage of participants; with the denominator for percentages being the number of participants entering the treatment period.

Rationale for estimand: It is important to document all safety issues that could potentially be attributable to the regimen, regardless of treatment non-compliance/discontinuation.

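### Protocol Section 10.3.1 ends its list of events that are not AEs with two bullets that, as printed, exclude related and unexpectedly intense events, against its own AE definition

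*Protocol*

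**What the plan says.** Protocol Section 10.3.1 gives a general definition of an AE, a list of events that meet it, and a list headed "Events NOT Meeting the AE Definition".

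- The general definition covers any untoward occurrence "temporally associated with the use of a study intervention, whether or not considered related to the study intervention".
- The list of events that qualify includes "Exacerbation of a chronic or intermittent pre-existing condition including either an increase in frequency and/or intensity of the condition". It also includes the consequences of a suspected interaction between interventions.
- The list of events that do not qualify ends with two bullets: "The event is, in the investigator's opinion, of greater intensity, frequency, or duration than expected for the individual participant, or" and "The investigator considers that there is a reasonable possibility that the event was related to the administration of the study intervention". No sentence between the heading and these bullets turns them into exceptions.

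Among the secondary safety endpoints in Protocol Section 3 is "Incidence of adverse events considered by the investigator to be possibly, probably or definitely related to study drug", overall and by drug. SAP Section 4.3.2.2.1 plans a separate summary of drug-related AEs for each of Microgynon and GSK3036656.

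**The concern.** The two closing bullets describe the usual reasons for recording an event, but they stand in the list of reasons for not recording one. Section 10.3.1 therefore gives an investigator two opposite instructions on the same event. A site that resolved the conflict in favour of the exclusion list would leave related or unexpectedly intense non-serious events out of the AE record. The tolerability description would then look better than it should.

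The study is small (about 20 enrolled) and open-label. Protocol Table 2 states that both earlier clinical studies it describes excluded females, so related events in women are new information here. An event that is never recorded leaves no trace in the database.

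**Working it through.** No arithmetic beyond a count applies, and the plan states no figure on this point. The check sets the passages side by side.

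**1. Does the definition control what is recorded?** Yes. Protocol Section 8.4 makes the investigator responsible for recording events that satisfy the AE or SAE definition, and points to Section 10.3 for it. Section 8.3.4 makes the recording of clinically significant laboratory findings, where there is no diagnosis, conditional on meeting the definitions in Sections 10.3.1 and 10.3.2. The list is therefore an operative rule and not background text.

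**2. The relatedness bullet against the rest of the protocol.**
- The general definition in Section 10.3.1 applies "whether or not considered related to the study intervention". The bullet makes a judgement of relatedness a ground for exclusion.
- The list of qualifying events covers suspected interactions between interventions. In a drug interaction study such an event would ordinarily be judged possibly related, so one section both includes and excludes it.
- The table of definitions treats an adverse drug reaction as a kind of adverse event, identified by the same reasonable-possibility test.
- Section 8.4 requires follow-up of AEs considered related. Section 8.4.1 requires collection of all AEs from the start of study intervention to Day 18. Section 10.3.4.3 requires a causality judgement for every AE. All three presuppose that a related event is still an AE.

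**3. The intensity bullet against the rest of Section 10.3.1.** It conflicts with the exacerbation item in the list of qualifying events. It also conflicts with the first two items of its own list, each of which brings an event back in when it is more severe than expected.

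**4. Which endpoints depend on the list?** Protocol Table 3 has eight safety endpoints.
- SAEs (1 endpoint): not affected. Section 10.3.2 defines an SAE from any untoward medical occurrence and does not use the AE exclusion list.
- PCI values for ECG, clinical chemistry, haematology and vital signs (4 endpoints): not affected. They come from measured values against the limits in SAP Section 6.2.3.
- Related AEs, grade 3 or higher AEs, and withdrawals due to AEs: 8 − 1 − 4 = 3 endpoints, exposed through their non-serious events.

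If the bullets are applied literally, the bias in these three is downward, because events can only be removed.

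**5. Could the analysis repair it?** No. SAP Section 4.3.2.2.1 works from recorded events and their onset dates, and SAP Section 4.3.2.2 does not impute missing safety data.

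**6. An illustration from the documents.** Protocol Table 2 reports one participant in Study 201214 with ventricular hypokinesia judged drug-related, and no cardiovascular SAEs in that study. In the present study echocardiography is scheduled only at screening, with repeats at the investigator's discretion, and it is not one of the four PCI domains. For a similar non-serious event, the AE record would be the main route into the safety endpoints.

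**The case against.** The strongest reply is that no careful investigator would follow the two bullets. Doing so means overriding the general definition a few lines above, the list of qualifying events, the collection rule in Section 8.4.1, the causality duty in Section 10.3.4.3, the definition of an adverse drug reaction and a named endpoint. Section 7.1.2 also asks for new clinically relevant ECG findings to be reported as AEs.

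The bullets do not read like exclusion items either. The other items name kinds of event or situation. These two are bare conditions, the first ending in a dangling conjunction, which suggests the tail of a sentence whose opening has gone. A lead-in that stands in the signed document but was lost when the PDF was read cannot be wholly excluded, although no gap or redaction mark appears there.

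Most of this stands. It shows what the sponsor intended, and it makes the harm conditional on literal application. It does not remove the contradiction from a section to which sites are sent in order to decide what to record.

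A reader might go further and infer that the sponsor means to exclude related events, or that the related-AE endpoint would have nothing left to count. The documents support neither. The provisions just listed show that related events are meant to be collected, and related serious events would still be captured through the SAE definition. A reader might also divide one participant by the number enrolled to obtain a loss in percentage points. That arithmetic fits any binary endpoint with the same denominator and measures nothing about this defect.

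**Conclusion.** The point holds as an internal inconsistency in the AE definition. It is not an error in any analysis choice: no estimand, model, analysis set or SAP rule is wrong.

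Its reach is three descriptive secondary endpoints of the eight for safety, with bias downward and confined to non-serious events that are related or more intense, frequent or prolonged than expected. How many events would be lost cannot be derived from the documents, since it depends on how many such events occur and on how sites read a self-contradictory section. The four primary PK comparisons, the sample size, the SAE endpoint and the PCI endpoints do not depend on it.

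The conclusion assumes that the bullets stand in the signed protocol without a lead-in, which the sponsor can confirm by looking at the page. The likely origin as a drafting slip lowers the chance of harm. The text is nevertheless wrong as written in a place that governs recording, and it should be corrected.

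**What to change.** Make one of two changes in Protocol Section 10.3.1:

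- delete the last two bullets from the list of events that do not qualify; or
- restore a lead-in stating that an event otherwise excluded by the list must be recorded as an AE when either condition applies.

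Either makes the section agree with its own general definition. The bullets should not be moved to the list of qualifying events as stand-alone criteria. That would suggest that relatedness or excess intensity is needed for an event to be an AE, which the general definition denies.

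Send a short note to sites, carry the same wording into the eCRF completion guidelines, and include the correction in the next amendment. The cost is a few lines of text. No visit, sample, participant or analysis changes.
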